### **4.3. Enrollment Process**

After informed consent is obtained, the required screening procedures are performed, and the results known, the site PI/designee will complete the enrollment form and send it to the Sponsor/designee, along with supporting documentation as listed in the study manual. After Sponsor/designee review, if eligible, the Sponsor/designee will assign a patient study number to the patient and inform the site PI/designee.

#### 4.4. **Withdrawal Criteria and Replacement of Patients**

Patients are free to withdraw from the study at any time for any reason; however, to the extent possible, all patients should continue to participate in the study once they have enrolled, even if they discontinue study drug. The Investigator also has the right to withdraw a patient from the study in case of events such as inter-current illness, AEs, progression, protocol violation, other procedures needed for treatment of their disease, or other medical conditions, administrative reasons or for other reasons (detailed in Section 4.4.1).

An excessive rate of withdrawals can render the study un-interpretable; therefore, unnecessary withdrawal of patients should be avoided. Should a patient decide to withdraw, all efforts will be made to complete and report the observations as thoroughly as possible. Reasons for all discontinuation of study drug and withdrawals from the study will be recorded. If a patient discontinues the study drug due to an AE, that AE must be evaluated to determine if it is a serious adverse event (SAE; see Section 10.1.2). The Investigator must report all SAEs to the Syneos Safety Department (the Sponsor's Safety Designee) on the SAE form within 24 hours from the point in time when the Investigator becomes aware of the SAE. The procedures described under 30 Days Post-Last Treatment (Section 7.3.2.2) will be performed upon discontinuation/withdrawal, whenever possible. If a patient withdraws consent, no further information will be collected after the study termination visit.

Normal study termination is defined as the 30 Days Post-Last Treatment visit in Section 7.3.2.2.

##### 4.4.1. **General Withdrawal Criteria**

Discontinuation of study drug and/or withdrawal from the study will occur if any of the following apply:

- The patient experiences disease progression requiring other therapy.
- The patient develops intolerable toxicity.
- The patient develops an intercurrent condition precluding further administration of cerdulatinib.
- The patient withdraws consent for further participation in the trial.
- The patient becomes pregnant.
- The patient fails to comply with study drug administration, dosing evaluations, or other requirements of the study.
- The patient needs a concomitant medication that makes the patient ineligible for further participation in the study.
- The Investigator believes it is no longer in the best interest of the patient to receive cerdulatinib.
- The Sponsor discontinues the trial.

**4.4.2. Specific Withdrawal Criterion and Replacement Procedure for Phase 1**

- Patients who discontinue from treatment prior to the completion of Cycle 1 or who do not receive at least 80% of the intended dose in Cycle 1 for reasons other than toxicity will be replaced. Dose escalation will not take place until the appropriate number of patients has completed Cycle 1 at the designated dose level.

**4.4.3. Specific Withdrawal Criteria and Replacement Procedure for Phase 2a**

- Patients who do not have at least 1 post baseline assessment for efficacy will be withdrawn from the study and may be replaced.
- Patients who are found to have protocol violations that substantially impair the evaluation of safety and efficacy may be replaced.

**4.5. Withdrawal and/or Replacement Criteria for Site or Principal Investigator**

The site or Principal Investigator may be withdrawn or replaced from the study due to poor compliance with the study protocol or poor accrual.

**4.6. Sponsor Study Discontinuation**

The Sponsor has the right to terminate the entire study or study cohorts at any time. Reasons for terminating the study or study cohorts may include, but are not limited to, the following:

- Excessive toxicity indicating a potential health hazard to patients.
- Poor patient enrollment.

The Sponsor will notify the Investigator if the study is placed on hold (or if individual cohorts are placed on hold), or if the Sponsor decides to discontinue the study or program.

**4.7 Protocol Violations and Deviations**

Protocol violations are defined as significant departures from protocol-required processes or procedures that affect patient safety or benefit potential, or confound assessments of safety or clinical activity. A protocol deviation is a departure from the protocol that does not meet the above criteria. Protocol violations or deviations may be grouped into the following categories:

- Enrollment criteria.
- Study activities (e.g., missed evaluations or visits, data verification issues).
- Noncompliance with dose or schedule, including dose calculation, administration, interruption, reduction, or delay, or discontinuation criteria.
- Investigational product handling, including storage and accountability.
- Informed consent and ethical issues.

## 5.0 TREATMENTS ADMINISTERED

Treatments administered during the study are listed below. Administration of study drug and related dose modifications are described in Sections 5.1 and 5.2 for cerdulatinib and in Section 6.2 for rituximab.

- Phase 1 (**closed**): single-agent cerdulatinib
- Phase 2a:
  - Cohorts 1, 3, 4, 5, and 6: single-agent cerdulatinib
  - Cohort 2: cerdulatinib and rituximab

### 5.1. Cerdulatinib Study Drug Administration

#### 5.1.1. General Instructions

Cerdulatinib may be taken with food, unless otherwise specified. Missed doses may be made up if given within 4 hours of the missed scheduled dosing time. Cerdulatinib may not be taken fewer than 8 hours prior to the next scheduled dose. Patients who vomit following administration of cerdulatinib should not repeat that dose of cerdulatinib but should resume study drug with the next scheduled dose. In the event of toxicity, dosing may be interrupted at the discretion of the treating physician until sufficient resolution of the toxicity is attained and then may be restarted at a lower dose level (see Section 5.2 for guidelines for cerdulatinib toxicity and subsequent dose modifications).

In order to assess cerdulatinib compliance, patients will be instructed to keep patient diaries to document self-administration of study drug doses, and will include documentation of time study dose was taken, any missed doses and reason(s) why missed, and/or any wasted doses and reason(s) why. The diary will be reviewed by the appropriate study staff during study visits.

#### 5.1.2. Phase 1 Cerdulatinib Dosing

##### 5.1.2.1. *Initial Dosing with Cerdulatinib*

Following screening and confirmation of eligibility, patients will be sequentially assigned to the next open dose cohort. For QD dosing regimens, to allow for single-dose PK assessments during the Phase 1 portion of the study, patients will take their first dose of cerdulatinib on Day 1 and their second and subsequent doses daily beginning on Day 4. During Part 1 of the study, cerdulatinib will be taken orally once daily in the AM. For BID dosing regimens, BID dosing can begin on Day 1.

The initial dose cohort will begin treatment at a dose of 15 mg po QD. Subsequent total daily dose levels that may be studied include 30 mg, 60 mg, 90 mg, 120 mg, and 150 mg daily. Intermediate or higher dose levels may be studied, as appropriate, given the safety and PK profiles of cerdulatinib observed during the ongoing conduct of this study. Depending on the

PK profile, twice-daily administration (BID) may be considered during the course of dose escalation. Single-dose PK assessment will not be conducted for BID cohorts. Increments of dose escalation will be adjusted as needed to accommodate available capsule strengths. Every effort should be made to administer study drug at the same times each day.

Patients who do not receive at least 80% of their cerdulatinib doses in the first 28 days of treatment (Cycle 1) due to non-compliance will be withdrawn from the study. Beyond Cycle 1, dose holds may be permitted for reasons not related to disease progression or drug-related toxicity (e.g., elective procedures, vacations) with the permission of the Sponsor's Medical Monitor.

Intra-patient dose escalation will not be permitted during Phase 1.

The dose-escalation scheme described in this and the following paragraph accords with the principles described by Le Tourneau et al [6]. One patient will be enrolled in each dose cohort until the first report of a Grade 2 or greater adverse event (AE). In the event of any Grade 2 or greater AE in the single patient, an additional 2 patients, for a total of 3, will be enrolled in that dose cohort, and all subsequent dose cohorts will follow a "3 + 3" design. Dose escalation will be in 100% increments until a drug-related adverse event of Grade 2 or greater severity occurs. Thereafter, dose escalation will be in increments of up to 50% as determined following review by the safety committee. If a dose-limiting toxicity (DLT) occurs in 1 of the first 3 patients in a cohort, that cohort will be expanded to at least 6 patients. If  $\leq 33\%$  of six or more patients in a cohort experiences DLT, dose escalation may proceed. If in any cohort 2 or more of the first 3 patients or  $\geq 33\%$  of patients in a cohort develop DLT, dose escalation will cease. That dose level will be declared intolerable, and either the prior dose level will be declared the MTD, and/or the cohort may be expanded to as many as 6 patients if fewer than 6 patients had previously been treated at that dose level in order to further characterize the PK and PD at that level. A total of 43 patients have been enrolled in the Phase 1 (escalation) portion of this study, and Phase 1 is now closed to enrollment.

All patients in a cohort must have been treated for 28 days (one cycle) prior to treatment of patients at the next higher dose level. In addition to DLTs defined below, the safety committee will also take into consideration the totality of available safety data in determining whether a given dose level should be deemed tolerable. Additional patients may be enrolled in individual cohorts if the Sponsor's Medical Monitor or safety committee deems it necessary to obtain additional safety information prior to proceeding with dose escalation. In addition, intermediate dose levels may be used to allow for further exploration of safety.

As of Amendment 4, Phase 1 dose escalation has concluded at 45 mg po BID (per Sections 1.5 and 3.1.2.2). The dose selected for Phase 2a is 35 mg po BID based on PK modeling and accumulated safety data (Section 3.1.2.2).

### 5.1.3. **Phase 2a Cerdulatinib Dosing**

Following confirmation of eligibility, patients will receive oral cerdulatinib at a starting dose of 30, 25, or 20 mg BID. Every effort should be made to administer study drug at the same time each day. The drug will be administered in cycles of 28 days with no days off therapy between cycles.

In the event of toxicity (see Section 5.2.1 for the definition of *toxicity*), dosing may be interrupted at the discretion of the Investigator until sufficient resolution of the toxicity is attained and then restarted at a lower dose level (dose modifications to cerdulatinib are summarized in Table 8). The lowest dose of cerdulatinib that may be administered is 15 mg BID.

Dosing information for rituximab is described in Section 6.2 (for Cohort 2, the combination cohort of cerdulatinib and rituximab).

## 5.2. **Dose-limiting Toxicity, Dose Modifications, and other Dosing/Monitoring Guidance**

### 5.2.1. **Cerdulatinib**

#### 5.2.1.1. ***Definitions of Dose-limiting Toxicity for Cerdulatinib during Phase 1***

DLT will be defined as any of the following toxicities, possibly or probably related to cerdulatinib, and clinically significant (in the judgement of the investigator) that occurs in the first 28 days (one cycle) of treatment. For patients to be evaluable for DLT, they must have received 80% of the doses in the first 28 days of Cycle 1, or been withdrawn from study therapy due to a drug-related toxicity. Patients who withdraw without meeting these criteria should be replaced. Toxicity will be graded according to the NCI-CTCAE v4.0.

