## **2.2. Endpoints**

### **2.2.1. Phase 1 Endpoints**

#### **2.2.1.1. Primary Endpoint**

- The primary safety endpoint will be the incidence of DLT by dose level.

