###### 3.1.1.1. Overall Description

*Patients:* The Phase 1 portion of the study will include patients with a histologically confirmed diagnosis of CLL/SLL or B-cell non-Hodgkin lymphoma.

*Design:* Eligible patients enrolled in sequential dose cohorts will receive once-daily, orally administered single-agent cerdulatinib at starting dose of 15 mg (15 mg po QD) in increasing dose levels until the MTD/MAD is identified. **An exception occurs on Days 2 and 3, during which patients on a QD schedule will not take study drug (see next paragraph).** If the MTD is not achieved, the highest studied dose will be declared the MAD and become the RP2D. (See [Table 3](#) for definitions of cancer types.)

To allow for a single-dose PK assessment, patients on a QD dosing regime will take their first dose of cerdulatinib on Day 1 and their second and subsequent doses daily beginning on Day 4. **They will not take cerdulatinib on Days 2 or 3.** Starting with Day 4, patients will receive cerdulatinib once daily for a total of 28 days (one cycle) to assess the MTD/MAD. Patients on BID dosing schedules can dosing begin on Day 1 and continue cerdulatinib without interruption (i.e., these patients will not skip any days of the cycle). If cerdulatinib is well tolerated, patients may continue to receive cerdulatinib at their assigned dose in the absence of disease progression, unacceptable toxicity, or meeting of any other withdrawal criteria (Section [4.4](#)).

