#### **Non-hematologic**

- Grade 3 or greater nausea, vomiting, or diarrhea if persistent despite optimal antiemetic or anti-diarrheal therapy.

- Grade 3 or greater increase in transaminases lasting > 5 days.
- Grade 3 or greater fatigue persisting > 7 days in the absence of any other underlying cause.
- Any other Grade 3 or greater non-hematologic toxicity (except fatigue as noted above) considered clinically significant by the investigator.
- Toxicity of any grade resulting in dose delay of more than 7 days.
- Toxicity resulting in study drug discontinuation prior to the completion of Cycle 1.

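### The DLT-evaluability rule has no route for a patient who has a DLT, is held and resumes, and the SAP leaves the denominator of the Phase 1 primary endpoint unsettled

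*Protocol*

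**What the plan says.** The Phase 1 primary endpoint is set in Protocol 2.2.1.1: "The primary safety endpoint will be the incidence of DLT by dose level".

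Protocol 5.2.1.1 then limits who can contribute to it. For patients to be evaluable, "they must have received 80% of the doses in the first 28 days of Cycle 1, or been withdrawn from study therapy" because of a drug-related toxicity. The next sentence adds: "Patients who withdraw without meeting these criteria should be replaced". SAP 7.8.1.1 repeats both sentences.

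The non-hematologic DLT list in the same protocol section includes "Toxicity of any grade resulting in dose delay of more than 7 days" and, as a separate item, "Toxicity resulting in study drug discontinuation prior to the completion of Cycle 1". Because discontinuation has its own item, the delay item must cover patients who restart.

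Protocol 4.4.2 handles the same 80% threshold differently. Phase 1 patients "who do not receive at least 80% of the intended dose in Cycle 1 for reasons other than toxicity will be replaced". A shortfall caused by toxicity is therefore not a ground for replacement.

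On the analysis side, SAP 7.8.1.1 opens by promising the number and percentage of patients with DLTs that the investigator recorded in the eCRF, by starting dose cohort. SAP 7.9 places every safety analysis in the safety population, which SAP 6 defines as patients with at least one dose. SAP 6 defines no DLT-evaluable set.

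**The concern.** The two evaluability routes are enough dosing, or withdrawal for toxicity. A patient whose DLT is a long hold, and who then resumes, is likely to miss both: the hold uses up the dosing allowance and there is no withdrawal. Taken at its word, the rule excludes patients because of the event it is meant to count. Such a patient is also not replaced under 4.4.2, so the cohort loses both a DLT and a patient.

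Other DLTs managed by a long enough interruption and a restart (Protocol 5.1.1 allows this in general terms) fall into the same gap, though the documents do not say how often that happened.

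The SAP does not say whether the repeated rule sets the denominator. One programmer could apply it and another could use all treated patients, and they would report different DLT percentages from the same data.

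**Working it through.** The documents give no expected DLT rate and no number of DLT-evaluable patients, so there is no plan figure to reproduce. The check counts doses.

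**Inputs.** The window is 28 days and the threshold 80% (Protocol 5.2.1.1). BID schedules 2 × 28 = 56 doses. On QD, Protocol 3.1.1.1 gives a dose on Day 1 and "their second and subsequent doses daily beginning on Day 4", so 28 − 2 = 26 doses fall in calendar Days 1 to 28; it is 28 if the window is read as 28 dosing days. The shortest whole-day delay that meets the DLT criterion is 8 days. I count each day of delay as that day's doses missed.

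**Step 1: allowance.** Doses required = 0.8 × scheduled, rounded up.

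| Schedule | Scheduled | Required | Most that can be missed |
|---|---|---|---|
| QD, 28 doses | 28 | 22.4 → 23 | 5 days |
| QD, Days 2–3 off | 26 | 20.8 → 21 | 5 days |
| BID | 56 | 44.8 → 45 | 11 doses (5.5 days) |

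**Step 2: 8 days' doses missed.**
- QD, 28 doses: (28 − 8)/28 = 71.4%
- BID: (56 − 16)/56 = 71.4%
- QD, 26 doses: (26 − 8)/26 = 69.2%

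**Step 3: start day.** A hold that starts on Day d and runs past Day 28 misses 29 − d days of the window.
- d = 23: 6 days missed, leaving 22/28 = 78.6% (QD with 26 doses: 20/26 = 76.9%; BID: 44/56 = 78.6%). Fails.
- d = 24: 5 days missed, leaving 23/28 = 82.1% (21/26 = 80.8%; 46/56 = 82.1%). Passes.

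For an 8-day hold starting on each of Days 2 to 28, 22 of the 27 start days (Days 2 to 23) fall below 80% on all three schedules. Every such hold that ends by Day 28 (starts on Days 2 to 21) fails.

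**Step 4: what each passage does with a patient held 8 days inside the window who resumes.**
- Evaluability sentence (Protocol 5.2.1.1, SAP 7.8.1.1): not evaluable.
- Replacement sentence beside it: does not apply, since the patient has not withdrawn.
- Protocol 4.4.2: not replaced, since the cause is toxicity.
- Protocol 5.1.2.1: not withdrawn, since an 80% shortfall leads to withdrawal only for non-compliance.
- SAP 7.8.1.1 opening sentence with SAP 7.9: counted in numerator and denominator.

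**Step 5: size if the evaluability sentence is applied literally.** Let p be the true DLT rate, h the share of DLTs that are holds with resumption (assumed; not in the documents), and q = 22/27 the share of those falling below 80% if start days are equally likely. The fraction removed is d = p·h·q, and the reported rate is (p − d)/(1 − d). For p = 1/3 and h = 25%: d = 0.333 × 0.25 × 0.815 = 0.068, and (0.333 − 0.068)/(1 − 0.068) = 28.5%.

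| True rate | h = 10% | h = 25% | h = 50% |
|---|---|---|---|
| 33.3% | 31.5% | 28.5% | 22.9% |
| 25% | 23.4% | 21.0% | 16.5% |

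**Step 6: size if all treated patients are used.** Hold-type DLTs stay in, so that bias is zero. But patients replaced under 4.4.2 for non-toxicity reasons took at least one dose and stay in too. With x DLTs, n adequately observed patients and m replaced patients without a DLT, the rate is x/(n + m), which is below x/n whenever x and m exceed zero. The protocol gives 43 dosed patients but no value for m.

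**The case against.** The strongest reply is that the SAP sentence specifying the DLT table does not use the evaluability rule at all. It counts eCRF-recorded DLTs by starting dose cohort, and SAP 7.9 supplies the safety population, so on that text no hold-type DLT is lost. The protocol's replacement and withdrawal provisions also leave the patient in the cohort. This stands as far as it goes: a low bias is not established, only possible. It does not settle the matter, because the same SAP subsection goes on to repeat the evaluability rule without saying what it governs, and because the safety population brings in the inadequately observed patients of Step 6.

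A reader might infer that a dose level was passed as tolerable because DLTs were dropped. The documents do not support that. Protocol 5.1.2.1 lets escalation proceed after expansion only on six or more patients, and 4.4.2 blocks it until enough patients have completed Cycle 1, so a cohort shrunk below six would not qualify. The committee was also to weigh all the safety data available. Both DLTs at 45 mg BID were counted and that regimen was judged not tolerated (Protocol 1.5). Phase 1 is closed.

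Two limits on the arithmetic also stand. It equates a dose delay with missed doses inside Cycle 1, whereas Protocol 4.7 lists interruption and delay as separate terms. And for DLTs other than the delay item, the effect depends on hold lengths that the current documents do not set for Phase 1.

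**Conclusion.** The gap is real: as written, the evaluability sentence excludes most patients whose DLT is a toxicity delay of more than 7 days followed by resumption. It conflicts with Protocol 4.4.2 and with SAP 7.9 and the opening of SAP 7.8.1.1. The SAP therefore offers two denominators for the Phase 1 primary endpoint, and each can lower the reported rate: one by dropping hold-type DLTs, the other by keeping inadequately observed patients.

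It would go too far to say that DLT incidence is biased low. That follows only if the evaluability sentence is used as the exclusion rule, and the size then depends on a share of hold-type DLTs that the documents do not give; the Step 5 figures are illustrations under assumed shares and equally likely start days. No lost DLT is documented, and no past escalation decision is affected. What is at stake is correct reporting of the primary endpoint in the combined clinical study report, for which SAP 1 says no formal Phase 1 analysis has yet been done.

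**What to change.** In SAP 7.8.1.1, define the DLT analysis set as patients who
- had any DLT in the first 28 days, or
- received at least 80% of planned doses in that window, or
- were withdrawn for drug-related toxicity.

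The 80% requirement then applies only to patients without a DLT. State that this set is the denominator of the DLT percentage, and add a line counting DLT patients who received less than 80%. State whether planned QD doses in the window number 26 or 28.

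Reconcile Protocol 5.2.1.1 and the repeated rule in SAP 7.8.1.1 with Protocol 4.4.2, SAP 7.9 and the opening of SAP 7.8.1.1. That should also cover the patient with a 6- or 7-day toxicity hold and no DLT (22/28 = 78.6% or 21/28 = 75.0%), who would be outside the set yet not replaced under 4.4.2.

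The cost is a short SAP edit before the Phase 1 tables are produced. It needs no new data and changes no dosing rule. The downside is that the reported DLT rate may be slightly less favourable.

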#### **Hematologic**

- Febrile neutropenia (ANC < 1,000/ $\mu$ L and temperature  $\geq$  38.5°C).
- Grade 4 neutropenia for > 5 days.
- Grade 4 thrombocytopenia with or without bleeding.
- Grade 3 thrombocytopenia with bleeding.
- Grade 4 anemia, unexplained by underlying disease.

